#### PROTOCOL SYNOPSIS

### **Study Number and Title:**

ASTX727-02: A Phase 3, Randomized, Open-Label Crossover Study of ASTX727 (Cedazuridine and Decitabine Fixed-Dose Combination) versus IV Decitabine in Subjects with Myelodysplastic Syndromes (MDS) and Chronic Myelomonocytic Leukemia (CMML)

**Investigational Drug:** ASTX727 (recently approved as INQOVI®) is a film-coated, oval, immediate-release tablet of a fixed-dose combination (FDC) of cedazuridine (E7727) (100 mg) and decitabine (35 mg) for oral administration.

Clinical Phase: 3

Study Centers Planned/Country: Multicenter, North America

### **Study Objectives:**

### **Primary Objective**

• To establish decitabine AUC equivalence of 5-day dosing between ASTX727 and IV decitabine.

### **Secondary Objectives**

To assess the following:

- Long-term safety and efficacy (response rate) of ASTX727.
- Long interspersed nucleotide elements-1 (LINE-1) demethylation.
- Additional pharmacokinetics (PK) parameters.

### Study Design and Investigational Plan:

This is a multicenter, randomized, open-label, 2-period, 2-sequence crossover study of ASTX727 versus IV decitabine. Adult subjects who are candidates to receive IV decitabine will be randomized in a 1:1 ratio to receive the ASTX727 FDC tablet Daily×5 in Cycle 1, followed by IV decitabine 20 mg/m² Daily×5 in Cycle 2, or the converse order. Adequate PK assessments from both cycles will be required for subjects to be evaluable for analysis of the primary endpoint. After completion of the first 2 treatment cycles, subjects will continue to receive treatment with ASTX727 in 28-day cycles until disease progression, unacceptable toxicity, or the subject decides to discontinue treatment or withdraw from the study.

### Study Population:

### **Inclusion Criteria**

Approximately 132 (at least 118 evaluable) subjects will be enrolled in this study at approximately 60 study centers in North America. Subjects must fulfill all of the following inclusion criteria:

- 1. Able to understand and comply with the study procedures, understand the risks involved in the study, and provide legally effective informed consent before the first study-specific procedure; specifically able to comply with the PK assessment schedule during the first 2 treatment cycles.
- 2. Men or women ≥18 years who are candidates to receive IV decitabine, ie, subjects with MDS previously treated or untreated with de novo or secondary MDS, including all French-American-British subtypes (refractory anemia, refractory anemia with ringed sideroblasts, refractory anemia with excess blasts, refractory anemia with excess blasts in transformation, and chronic myelomonocytic leukemia [CMML]), and subjects with MDS International Prognostic Scoring System (IPSS) int-1, -2, or high-risk MDS.
- 3. Eastern Cooperative Oncology Group (ECOG) performance status of 0 to 1.
- 4. Adequate organ function defined as follows:
  - a) Hepatic: Total or direct bilirubin ≤2 × upper limit of normal (ULN); AST/SGOT and ALT/SGPT <2.5 × ULN.
  - b) Renal: serum creatinine  $\leq 1.5 \times \text{ULN}$  or calculated creatinine clearance or glomerular filtration rate  $>50 \text{ mL/min}/1.73 \text{ m}^2$  for subjects with creatinine levels above institutional normal.
- 5. No major surgery within 30 days of first study treatment.
- 6. Life expectancy of at least 3 months.
- 7. Women of child-bearing potential must not be pregnant or breastfeeding and must have a negative pregnancy test at screening. Women of non-childbearing potential are those who have had a hysterectomy or bilateral oophorectomy, or who have completed menopause, defined as no menses for at least 1 year AND either age ≥65 years or follicle-stimulating hormone levels in the menopausal range.
- 8. Subjects and their partners with reproductive potential must agree to use effective contraceptive measures during the study and for 3 months after the last dose of study treatment. Effective contraception includes methods such as oral contraceptives or double-barrier method (eg, use of a condom AND diaphragm, with spermicide).

#### **Exclusion Criteria**

Subjects meeting any of the following criteria will be excluded from the study:

- 1. Prior treatment with more than 1 cycle of azacitidine or decitabine.
- 2. Hospitalization for more than 2 days for documented febrile neutropenia, pneumonia, sepsis, or systemic infection in the 30 days before screening.
- 3. Treatment with any investigational drug or therapy within 2 weeks of study treatment, or 5 half-lives, whichever is longer, before the first dose of study treatment, or ongoing clinically significant adverse events (AEs) from previous treatment.
- 4. Cytotoxic chemotherapy or prior azacitidine or decitabine within 4 weeks of first dose of study treatment.
- 5. Concurrent MDS therapies, including lenalidomide, erythropoietin, cyclosporine/tacrolimus, granulocyte-colony stimulating factor (G-CSF), granulocyte-macrophage colony-stimulating factor, etc. (Prior treatment with these agents is permitted, provided that completion is at least 1 week before the first dose of study treatment.)
- 6. Poor medical risk because of other conditions such as uncontrolled systemic diseases, active uncontrolled infections, or comorbidities that may put the patient at risk of not being able to complete at least 2 cycles of treatment
- 7. Known significant mental illness or other condition, such as active alcohol or other substance abuse or addiction, that in the opinion of the investigator predisposes the subject to high risk of noncompliance with the protocol.
- 8. Rapidly progressive or highly proliferative disease (total white blood cell count of  $>15 \times 10^9/L$ ) or other criteria that render the subject at high risk of requiring intensive cytotoxic chemotherapy within the next 3 months.
- 9. Life-threatening illness or severe organ system dysfunction, such as uncontrolled congestive heart failure or chronic obstructive pulmonary disease, or other reasons including laboratory abnormalities, which, in the investigator's opinion, could compromise the subject's safety, interfere with the absorption or metabolism of ASTX727, or compromise completion of the study or integrity of the study outcomes.
- 10. Prior malignancy, except for adequately treated basal cell or squamous cell skin cancer, in situ cervical cancer, prostate cancer or breast cancer under control with hormone therapy, or other cancer from which the subject has been disease free for at least 2 years.
- 11. Hypersensitivity to decitabine, cedazuridine, or any of the excipients in ASTX727 tablets or IV decitabine.

# **Study Treatment:**

Investigational medicinal product (IMP): ASTX727 tablet with ~240 mL (8 fluid oz) water Daily×5 every 28 days. Subjects must fast from food (clear liquids are allowed) 2 hours before and 2 hours after administration. No adjustment of dose for weight or body surface area will be made.

Reference product: IV decitabine 20 mg/m^2 as a 1-hour IV infusion Daily×5.

### Study Endpoints:

#### **Primary Endpoint**

Comparison between ASTX727 and IV decitabine:

• Total 5-day AUC exposures of decitabine after treatment with ASTX727 versus IV decitabine.

# **Secondary Endpoints**

- Safety as assessed by AEs, concomitant medications, physical examination, clinical laboratory tests (hematology and serum chemistry), vital signs, ECOG performance status, and electrocardiogram (ECG).
- Maximum %LINE-1 demethylation.
- Additional secondary PK parameters.
- Clinical response (complete response [CR], marrow complete response [mCR], partial response (PR), and hematologic improvement [HI]) based on International Working Group (IWG) 2006 MDS response criteria.
- Red blood cell (RBC) or platelet transfusion independence (TI).
- Leukemia-free survival, defined as the number of days from the date of randomization to the date when bone marrow or peripheral blood blasts reach ≥20%, or death from any cause.
- Overall survival (OS), defined as the number of days from the date of randomization to the date of death from any cause.

### Study Assessments and Procedures:

Study evaluation visits will occur on Days 1-5, then weekly, in Cycles 1 and 2. Bone marrow samples will be collected from subjects at Screening or within 21 days before Cycle 1 Day 1; on or before Day 1 of Cycles 3, 5, and 7, then every 3 months in first year and every 6 months thereafter. A manual differential of the myeloid cells in bone marrow will be performed with a minimum of 100 cells counted and a specific myeloblast percent generated. Complete blood count and differential will be obtained weekly during Cycles 1 and 2 then biweekly in Cycles ≥3, with specific output being hemoglobin, platelet count, white blood cell count and percent neutrophils (percent polymorphonuclear neutrophils and bands) or an absolute neutrophil count, and percentage of blasts. QTc interval will be assessed via routine ECG at Screening and on Day 3 of Cycles 1 and 2. The severity (intensity) of AEs will be graded according to the National Cancer Institute (NCI) Common Terminology Criteria for Adverse Events (CTCAE) for Cancer Clinical Trials, version 4.03.

#### **Pharmacokinetics Assessments:**

The schedule for PK assessments in Cycles 1 and 2 is as follows:

- ASTX727 cycle: predose on Days 1 through 5; serial collections on Days 1, 2, and 5; collection on Day 3 at 3 hours.
- IV decitabine cycle: predose on Days 1 and 5; serial collections on Days 1 and 5; collection on Day 3 before end of infusion.

### **Efficacy Assessments:**

Peripheral blood and bone marrow aspirate or biopsy will be collected and used for response assessments and assessment of leukemic transformation. Bone marrow aspirate or biopsy will be performed at Screening (or within 21 days before Cycle 1 Day 1), on or before Day 1 of Cycles 3, 5, 7, then every 3 months during the first year and every 6 months thereafter. Transfusion (blood and platelet) requirements will be recorded monthly. Survival status will be monitored and documented throughout the study.

### Pharmacodynamic Assessments

LINE-1 methylation (in blood) will be measured at the following time points:

- Predose on Day 1 of Cycles 1, 2, and 3.
- Days 8, 15, 22 of Cycles 1 and 2.

### **Safety Assessments:**

Safety will be assessed by subject reported and investigator observed AEs, along with concomitant medications, physical examination, clinical laboratory tests (hematology, serum chemistry, urinalysis), vital signs, ECOG performance status, and ECG.

### Sample Size and Statistical Analyses:

# Sample Size Calculation:

In a standard 2-period, 2-sequence crossover design under a 1:1 randomization ratio, all treated subjects with sufficient PK data will be included in the Primary Endpoint PK Analysis Set. Complete PK will require subjects to be successfully dosed and samples to be correctly collected and tested from a minimum of Day 1 and Day 2 or 5 in the ASTX727 cycle, and Day 1 or 5 in the IV decitabine cycle. The 5-day AUC will be calculated from all complete PK data sets in a cycle. A total of 118 subjects in the Primary Endpoint PK Analysis Set included in the 2 one-sided equivalence tests for the geometric mean ratio of ASTX727 5-day AUC relative to IV decitabine 5-day AUC will provide 90% power at the statistical significance level of 0.05, when the true ratio of geometric means is 1.0, the coefficient of variation (CV) under an unlogged scale is 0.55, and the 90% confidence interval (CI) equivalence limits for the ratio of geometric means are 0.8 and 1.25. Assuming 10% of subjects may not be evaluable in the study, approximately 132 subjects will need to be randomized.

### **Primary Pharmacokinetics Endpoint Analysis:**

The primary endpoint analysis will include data from the following time points to calculate 5-day AUC:

- ASTX727 AUC: Days 1, 2, and 5.
- IV decitabine AUC: Days 1 and 5.

PK exposure parameters will be estimated for all PK-evaluable subjects based on noncompartmental analysis. The primary endpoint of decitabine 5-day AUC will be analyzed in the log scale using the mixed effect model including fixed effects of sequence, period, and treatment, and a random effect of subject within sequence. A 90% CI for the geometric mean ratio of decitabine 5-day AUC0-t will be obtained by applying the exponential function on the 2-sided 90% CI for the difference of mean decitabine 5-day AUC between ASTX727 and IV decitabine in

the log scale from the mixed effect model. The study will be claimed positive if the 90% CI for the geometric mean ratio is contained within the interval (0.8, 1.25).

### **Secondary Endpoint Analyses:**

#### Safety

The Safety Analysis Set will include all subjects who received any amount of study treatment. Safety will be assessed by incidence, grade, and seriousness of AEs. AEs will be coded using Medical Dictionary for Regulatory Activities (MedDRA) and graded according to the NCI Common Terminology Criteria for Adverse Events (CTCAE) for Cancer Clinical Trials version 4.03. Treatment exposure, AEs including relatedness and severity, serious AEs (SAEs), and reasons for treatment discontinuation will be summarized. Concomitant medication will be coded using the WHO Drug Dictionary.

#### Efficacy

Efficacy endpoints will be analyzed for subjects in the Efficacy Analysis Set, defined as the set of all subjects who received at least one full dose (day) of study treatment. Proportions of clinical responses will be calculated for subjects in the Efficacy Analysis Set, while TI rates will be calculated based on subjects who are transfusion dependent at baseline. The 95% Wald CIs will be provided for clinical response rates and TI rates. Leukemia-free survival and OS will be presented using Kaplan-Meier estimates along with 95% CIs for medians.

#### **Pharmacokinetics**

Decitabine PK parameters  $AUC_{0-inf}$ ,  $C_{max}$ ,  $T_{max}$ , apparent clearance (CL/F), apparent volume of distribution (Vd/F), and apparent half-life ( $t_{1/2}$ ) are of secondary interest and will be reported with  $AUC_{0-t}$  where applicable. The PK parameters of cedazuridine and cedazuridine-epimer will be also reported. The secondary endpoint analysis will also include population PK for evaluation of various covariates and exposure-response.

#### **Pharmacodynamics**

All treated subjects with evaluable %LINE-1 data will be included for analysis. Evaluable pharmacodynamic (PD) samples will include Day 1 and at least Day 8 or Day 15 methylation results. To avoid the confounding effects of differing baselines in Cycle 2 vs Cycle 1 observed in study ASTX727-01, subjects will be compared for each of the 2 cycles separately, thus limiting the evaluation to interpatient comparisons in each of the 2 cycles. The 95% CI for the difference of mean maximum %LINE-1 demethylation between ASTX727 and IV decitabine in Cycle 1 will be generated using an analysis of variance (ANOVA) model. The 95% CIs for the maximum %LINE-1 demethylation will also be generated for ASTX727 and IV decitabine, respectively.

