# 7.6 Guidelines for Adjusting or Withholding Study Treatment

It is important that Cycles 1 and 2 are given at full dose (safely) to allow for proper assessment of exposure after ASTX727 and IV decitabine administration. Contact the Astex medical monitor if considering reducing the dose in the first 2 cycles.

Dose delays up to 2 weeks for recovery of blood counts from drug-related myelosuppression are acceptable. Delays beyond 2 weeks in the first 2 cycles must be approved by the medical monitor. Subjects whose therapy is interrupted during dosing days of ASTX727 in the first 2 cycles may not be evaluable for assessment of the primary endpoint unless treatment can be restarted on a later date (after agreement by the medical monitor) in a manner that will allow AUC assessment (see Section 11.2.2 and Section 11.6). Dosing should be delayed in the presence of non-hematologic toxicities (serum creatinine equal or greater than 2 mg/dL; SGPT or bilirubin equal or greater than 2 times the ULN), or active or uncontrolled infection until these toxicities are resolved.

Beginning with Cycle 3, dose delays to allow recovery of blood counts from drug-related myelosuppression are allowed at the discretion of the investigator. If there is a need for dose

reduction starting from Cycle 3, ASTX727 treatment may be reduced to 4 days. Additional dose reductions may be applied by further reducing treatment to 3 days. Dose reductions should be considered if myelosuppression is suspected to be drug-related rather than disease-related. Transient reductions in blood counts on Day 15 (expected maximal drug effect) followed by a recovery trend by Day 28 may be indicative of a drug-related effect, whereas stable counts or improvements in counts by Day 15 followed by reduction by Day 28 is indicative of a disease effect that is being improved by the drug on Day 15. In the event of drug-related count suppression, a dose reduction in consultation with the medical monitor may be considered to allow the patient to achieve a complete or partial response.

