## 7.0 STATISTICAL ANALYSIS

Unless otherwise specified, all statistical tests and confidence intervals (CIs) described in this document will be two-sided with alpha = .05. The SAS® statistical package (version 9.4 or a later version) will be used for the analyses.

The first dosing date is defined as the first date the subject received any study treatment. Subject disposition, demographics, and baseline characteristics will be summarized by treatment sequence and all subjects combined (Total). Adverse events (AEs) will be summarized by actual treatment received at the onset of the AE (Section 7.6.2). Efficacy analyses, laboratory tests, vital signs, ECG, and ECOG performance status will be summarized by treatment sequence and all subjects combined (Total), unless otherwise specified.

The following data listings by study center and subject ID will be provided: screened subjects (with reason for screen failure), disposition (with reasons for discontinuation of treatment and withdrawal from study), important protocol deviations, demographic and baseline characteristics, study drug administration, individual efficacy data, subjects excluded from the efficacy analysis, AEs, all deaths (including primary cause of death), serious adverse events (SAEs), other significant AEs (including treatment discontinuation due to AEs), concomitant medications, and the protocol specified laboratory measurements. Additional data listings may be generated to support other relevant discussions in Clinical Study Report.

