### **7.4 Pharmacodynamic (LINE-1) Analyses**

The PD (LINE-1) Analysis Set (Section 5.6) will be used for analyses of LINE-1 methylation. Since LINE-1 methylation levels often do not completely return to baseline by Day 28 of Cycle 1, and to avoid the confounding effects of differing baselines in Cycle 2 vs Cycle 1, subjects will be compared for each of the 2 cycles separately using the baseline values prior to each cycle, thus limiting the evaluation to interpatient comparisons in each of the 2 cycles.

For each of Cycles 1 and 2, LINE-1 methylation data will be summarized descriptively (using mean, standard deviation, standard error, median, minimum and maximum) by visit and treatment. Descriptive statistics for maximum %LINE-1 demethylation will be summarized by treatment.

In addition, the 95% CIs for mean maximum %LINE-1 demethylation in Cycles 1 and 2 will be provided for ASTX727 and IV decitabine, respectively. The 95% CI for the difference in mean

maximum %LINE-1 demethylation between ASTX727 and IV decitabine in Cycles 1 and 2 will also be generated based on an analysis of variance (ANOVA) model with treatment as factor.

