## 7.6.2 Adverse Events

Adverse events reported by study subjects or observed by investigators will be mapped to the appropriate System Organ Class (SOC) and Preferred Term (PT) according to the Medical Dictionary for Regulatory Activities (MedDRA). Severity of AEs will be graded using Common Terminology Criteria for Adverse Events (CTCAE) version 4.03.

Treatment-emergent AEs (TEAEs) are defined as events that first occurred or worsened on or after the date of the first dose of study treatment until 30 days after the last dose of study treatment or until the start of a post-treatment alternative anti-leukemia treatment, whichever occurs first, with the following exceptions: events that occurred after 30 days beyond the last dose of study treatment or the start of a post-treatment alternative anti-leukemia treatment will also be considered treatment-emergent if the events are both serious and related to the study treatment. For the purpose of determining whether an AE is a treatment-emergent AE, incomplete AE start and stop dates will be imputed conservatively following the data programming conventions as detailed in the Astex Data Programming Standards.

All AE data collected in the study database with an AE start date on or before the data cutoff date will be included in the data listings, including those that are not treatment emergent. Only TEAEs will be included in the AE summary tables.

An overall safety summary table containing counts and percentages of subjects with any AE, any AE Grade  $\geq 3$ , AE leading to treatment discontinuation, any SAE, and subcategories of SAEs (death vs not death) will be produced.

Related events are those that the Investigator considered to be related to study treatment as described in the study protocol. All summaries of AEs will be made separately in the following groups:

- IV decitabine in Cycle 1 or Cycle 2.
- ASTX727 in Cycle 1 or Cycle 2.
- ASTX727 in Cycle 3 or later.
- Total for ASTX727.
- Total for the AML study.

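### AML SAP 7.6.2 pools each product's adverse events over Cycles 1 and 2 with no by-cycle table, so delayed Cycle 1 events can be counted under the other product

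*Protocol*

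**What the plan says.** **LINE-1.** The protocol (Synopsis, Pharmacodynamics; repeated in 11.9) states that "subjects will be compared for each of the 2 cycles separately, thus limiting the evaluation to interpatient comparisons in each of the 2 cycles". Its stated reason, "To avoid the confounding effects of differing baselines in Cycle 2 vs Cycle 1 observed in study ASTX727-01", is only that the baselines differ. AML SAP 7.4 keeps the same design and is more explicit about the cause: "LINE-1 methylation levels often do not completely return to baseline by Day 28 of Cycle 1".

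**Adverse events.** AML SAP 7.0 sets the attribution rule: "Adverse events (AEs) will be summarized by actual treatment received at the onset of the AE". Section 7.6.2 then requires every AE summary to be made in five groups. The two that set oral against IV are "IV decitabine in Cycle 1 or Cycle 2" and "ASTX727 in Cycle 1 or Cycle 2"; the other three are ASTX727 from Cycle 3, all ASTX727, and the whole AML study. No AE table is limited to Cycle 1, split by cycle or split by sequence. Carry-over of AEs is not discussed.

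**Timing rules.** In SAP 7.6.2 an event is treatment-emergent if it is new or worsened between the first dose and 30 days after the last dose (or the start of other anti-leukemia treatment, if sooner). Later events still count if they are both serious and related. Protocol 4.2 justifies the washout by the expected absence of both compounds before the first Cycle 2 dose. Protocol 7.6 adds: "Dose delays up to 2 weeks for recovery of blood counts from drug-related myelosuppression are acceptable".

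**Scope.** SAP 1.0 limits the document to AML subjects and refers to a separate SAP for MDS/CMML. Protocol 11.8 says that AEs will be summarised according to the treatment period in which they occur, and defines no pooled columns.

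**The concern.** The two pooled columns are the only planned AE contrast between oral and IV decitabine within the trial. In a two-period crossover, an event that the Cycle 1 product causes but that starts in Cycle 2 goes to the Cycle 2 product under an onset rule. Randomising 1:1 to sequence balances a pure period effect across the products, but it does not undo this misattribution.

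The washout argument in protocol 4.2 concerns drug concentration. That is the right argument for the AUC endpoint, but it says nothing about delayed toxicity. The documents themselves recognise effects that outlast the drug: a methylation effect that is often still present at Day 28, and a 30-day window for treatment-emergent events.

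At stake is how far the descriptive AE tables can support a statement that the two products have similar tolerability. If carry-over is present and proportional to each product's own risk, the pooled columns would look more alike than the products are. Cycle 1 is the one period in which no study product has gone before, and the reader of the tables would not be able to see it.

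**Working it through.** The plan states no figure on this point, so there is none to reproduce. The check has four parts.

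**1. Does the window reach Cycle 2?** Inputs: last Cycle 1 dose on Day 5; 28-day cycles; 30 days after last dose (SAP 7.6.2).
- Day 5 + 30 = Day 35.
- Without delay, Cycle 2 Day 1 is Day 29, so Day 35 is Cycle 2 Day 7.
- With a delay of 7 days, Cycle 2 Day 1 is Day 36 and the overlap is gone.

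The SAP applies the 30 days to the last dose of study treatment overall, not to each product. The calculation applies the same length to the Cycle 1 product. On that basis an event in the first week of an undelayed Cycle 2 lies within 30 days of the Cycle 1 product but is counted only under the other one.

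**2. How much could the contrast shrink?** The documents give neither AE risks nor a carry-over rate. Assume equal numbers in the two sequences, true per-cycle risks pA and pB, D = pA − pB = 15 points, and a carry-over share c of 0.2 to 0.4.

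*Replacement:* a share c of Cycle 2-onset events belongs to the Cycle 1 product, in place of the current product's own.
- Cycle 2 difference = [(1−c)pA + c·pB] − [(1−c)pB + c·pA] = (1−2c)D.
- Pooled difference = ½D + ½(1−2c)D = (1−c)D.

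*Addition:* a share c of the previous product's risk is added among subjects without an event of the current product.
- Cycle 2 difference = [pA + c·pB(1−pA)] − [pB + c·pA(1−pB)] = (1−c)D.
- Pooled difference = ½D + ½(1−c)D = (1−c/2)D.

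| c | Cycle 1 only | Pooled, replacement | Pooled, addition |
|---|---|---|---|
| 0.2 | 15 | 12 | 13.5 |
| 0.4 | 15 | 9 | 12 |

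**3. Is the direction certain?** Take assumed risks of 30% and 20%, so the true difference is 10 points and the risk ratio 1.50.
- *Carry-over proportional to own risk (addition):* c = 0.10, 0.25 and 0.50 give differences of 9.5, 8.75 and 7.5 points and risk ratios of 1.45, 1.38 and 1.29. Both measures shrink.
- *Equal carry-over in both sequences:* adding 5 points to each product's Cycle 2 risk gives 32.5% against 22.5%; adding 10 points gives 35% against 25%. The difference stays at 10 points, while the risk ratio falls to 1.44 and 1.40.
- *No recount of ongoing events:* a Cycle 1 event that persists without worsening is not new in Cycle 2. If all Cycle 1 events persisted, and events under the two products were independent, the Cycle 2 risks would be 30% × (1 − 0.2) = 24% and 20% × (1 − 0.3) = 14%. The pooled columns would show 27% against 17%: still 10 points, with the risk ratio up from 1.50 to 1.59.

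The direction therefore depends on the mechanism and on the measure.

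**4. What would Cycle 1 alone deliver?** With the 85 randomised AML subjects of SAP 4.0 (42.5 per group) and the same assumed risks, the 95% half-width is 1.96 × √[(0.3×0.7 + 0.2×0.8)/42.5] = 0.183, about 18 points.

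**The case against.** The case on the other side is substantial, and most of it limits the point without removing it.

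- **LINE-1 and AEs differ in kind.** Demethylation is measured against a baseline taken before each cycle, so a shifted baseline distorts the endpoint directly. AE incidence is not a change score. Handling the two differently is not in itself a contradiction. This stands. A reader might infer from the LINE-1 text that AEs are known to carry over, but persistence of a methylation marker does not show that, and no section of either document says so.
- **The protocol's account of blood counts points to the product's own cycle.** Section 7.6 puts the expected maximal effect at Day 15 with a recovery trend by Day 28. The permitted delay also lets Cycle 2 wait, and events arising during the wait precede the other product. This stands as mitigation, and it is why the size of any carry-over should not be presumed large. It does not cover a Cycle 2 that starts on schedule.
- **The comparison is not a stated objective.** The safety objective is long-term safety of ASTX727, the trial is a PK bridge, and the columns are descriptive. Nor is AE incidence the only safety material split by product: SAP 7.6.5 summarises vital signs by visit and treatment group, and QTc against exposure is analysed separately. This lowers the weight of the point. The pooled columns nevertheless remain the only planned AE contrast of oral against IV.
- **Cycle 1 alone is imprecise.** A half-width of about 18 points is larger than the 15-point difference in the illustration. This stands against making Cycle 1 the sole basis for comparison, but not against showing it.

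**Conclusion.** The point holds for the AML SAP, as a gap in presentation with a cheap remedy. Section 7.6.2 pools both cycles for each product, the onset rule can place a delayed Cycle 1 event under the other product, and nothing in the planned tables would let a reader see whether this happened. The effect can attenuate the oral-versus-IV AE contrast. A true 15-point difference would appear as 9 to 12 points under replacement, or 12 to 13.5 points under addition. These figures rest on an assumed c of 0.2 to 0.4 and balanced sequences; the documents supply neither c nor the AE risks.

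Two stronger readings are tempting and are not supported:
- *That pooling does pull the two AE profiles together.* Equal carry-over leaves the absolute difference unchanged, and the rule against recounting ongoing events moves the risk ratio away from 1. Attenuation is possible but not established.
- *That the MDS/CMML analysis has the same fault.* Its SAP was not supplied. Protocol 11.8 specifies no pooled columns, and its wording by treatment period is compatible with a split by cycle. No error is shown there.

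**What to change.** In AML SAP 7.6.2:
- Keep the existing pooled columns.
- Add ASTX727 and IV decitabine AE columns split into Cycle 1 and Cycle 2.
- Present the Cycle 1 columns alongside the pooled ones as the contrast free of earlier study product.
- Add a sentence stating the attribution limit: assignment follows the product received at onset, so a delayed effect of the Cycle 1 product may appear under the Cycle 2 product.

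The cost is SAP wording and extra table columns from data already held, with no new assessments. The downside is precision. The Cycle 1 columns hold about half the subject-cycles of the pooled columns and, at the assumed risks, carry a half-width of about 18 points. They should be read as estimates only, and a wide interval in Cycle 1 should not be taken as evidence of similarity or of difference.
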